individualized by first having participants complete a web-based, interactive interview, using an MI framework, to explore what is particularly meaningful to them and how PA is consistent with those goals. After obtaining personalized information about meaning and PA goals, the web-based app will generate personalized messages that will be delivered as **ecological momentary interventions** to patients via text. A recent meta-analysis shows that text messages are an effective and flexible intervention strategy to increase PA.⁵⁸ MAP to Health's web-based interview plus text message modality (a) can flexibly deliver ecological momentary interventions to enhance meaning salience, (b) is resource-sparing, and (c) can be scaled up to a large audience without requiring interventionists or continued software maintenance (like smartphone apps).

Figure 3. Conceptual Model Integrating SDT and Meaning to Increase PA.

ii. Web-based Interview

The intervention begins with a web-based interview that guides participants through a structured behavior change clinical interview. Participants will log in to a web-based portal with a unique login and password. The interactive interview will: (1) provide an overview of the program; (2) gather information about past physical activity experience; (3) provide a rationale for connecting physical activity to meaning; (4) guide participants through a life values assessment to rank values in order of meaningfulness and gather details about the top 3 most meaningful areas; (5) make the explicit

connection between health and meaning; (6) identify how current behavior does not match with meaning or physical activity goals; (7) identify opportunity for physical activity; (8) guide participants in setting SMART goals for activity (Specific, Measurable, Attainable, Realistic, Timely); (9) elicit barriers and spur problem solving; and (10) summarize lessons learned and preview next steps. The initial interview will be designed to last 30 to 45 minutes. The information gathered from the interview will be used to program the personalized text messages (see next section).

iii. Text Messages

For 8 weeks after the initial interview, participants will receive text messages on their personal phones. The texts are designed to be delivered at times participants previously noted they will have an opportunity to be active (up to twice per day) and will incorporate personalized messages about meaning (e.g., For a person who derives meaning from work; “Good morning! Ready to go to the gym? Remember that being more active can help you take care of your health and be more efficient at work.”). These “just-in-time” messages will pair meaning with PA to (1) increase PA; (2) increase meaning salience; and (3) support basic psychological needs satisfaction to, in turn, internalize motivation to engage in PA.

iv. Weekly Activity Scheduling

Each week, participants will be prompted to log in to the web-based platform to update their physical activity schedule in the calendar for the coming week. Participants will have the option of carrying forward the previous week’s schedule and modifying it as they see fit. Weekly scheduling ensures that participants continue to actively plan for physical activity and that text messages are sent at appropriate times.

e. Outcome and Variable Definitions

i. Eligibility Screening

1. EHR screening data. Data will be collected from the EHR to determine eligibility for a pool of potentially eligible individuals. This will include information on demographic characteristics (e.g., age, race, ethnicity, sex), most recent height and weight (BMI), diagnoses (e.g., cancer, cardiovascular disease, dementia, mental health and substance use disorders), and residential information (e.g., residing in a nursing home or long-term care facility). Individuals who are recruited through emails or huddle announcements will complete a self-report survey that will assess the same information.
2. Self-reported Physical Activity. In the screening process, potentially eligible individuals will be asked to complete Godin’s Leisure Time Exercise Questionnaire (GLTEQ)⁵⁹ to assess recent moderate to vigorous physical activity (MVPA). Individuals are asked to think about a typically 7-day period (week) and how many times they exercise for more than 15 minutes per time for each type of activity (strenuous, moderate, or mild exercise). Individuals then estimate the total number of minutes per week they engage in each type of exercise. Individuals who exercise between 10 and 90 minutes per week of MVPA (mild exercise does not count) will be eligible for this study.
3. Intentions to be Physically Active. In the screening process, potentially eligible individuals will answer one question about intentions to increase physical activity: “Do you intend to increase your physical activity in the next 30 days?” Individual who answer “yes” will be eligible for this study.
4. Physical Activity Readiness. The Physical Activity Readiness Questionnaire (PAR-Q)⁶⁰ will be used to assess medical or physical contraindications to participate in physical activity. The PAR-Q has 6 questions that assess situations in which it may be unsafe to start a physical activity program without the supervision of a physician (e.g., Do you feel pain in your chest when you do physical activity?). If individuals answer “yes” to any one of the questions, they will not be eligible for the study.
5. Alcohol Use Disorders Screening. The Alcohol Use Disorders Identification Test – Consumption (AUDIT-C)⁶¹ is a 3-item screener that assesses whether someone may be engaging in problematic alcohol use. Individuals answer the frequency and volume of alcohol that they

typically drink on a scale from 0 to 4, with higher scores corresponding to greater frequency or volume of consumption. Items are summed for a total score. Individuals who score above the cut-point (>7) will be ineligible for this study.⁶²

ii. Measures Used in Both Phase 1 and Phase 2

1. Demographic questionnaire. Participants will complete self-report measures of demographic characteristics, including gender, age, race, ethnicity, marital status, employment status, education, and annual income.
2. Technology Acceptance. Participants will answer 10 questions rating the extent to which they found the MAP to Health intervention easy to use (4 items) and useable (4-items) and their intentions to use the intervention in the future (2 items). Items were based on previous research^{53,57} and modified for the purposes of this study. Participants will rate each item on a scale from 1 (strongly disagree) to 5 (strongly agree). Items will be averaged within each subscale (ease of use, usability, and intentions to use).
3. Intervention Fidelity to Theory. The Intervention Fidelity to Theory (IFT) questionnaire is a 14-item questionnaire that assesses the extent to which the MAP to Health intervention adheres to the theoretical foundations of supporting autonomy, competence, and relatedness and prompts meaning salience.⁵⁰ Participants rate the extent they agree with each item on a scale from 1 (strongly disagree) to 5 (strongly agree). Items will be averaged within each subscale for a total score.
4. Intervention Acceptability and Feedback. In both phases, participants will be asked to respond to a series of open-ended questions asking about their experiences with the intervention (either the interview alone or the interview plus text messages) and the research process.

iii. Measures Used in Phase 1 Only

1. Text Message Acceptability. Participants will rate each one of a list of generated text messages (up to 14 messages) on whether they are a good fit for them (Yes/No). If participants say “No” to any message, they will be prompted to give feedback on how that message could be improved.

iv. Measures Used in Phase 2 Only

1. Physical Activity History. Physical activity history will be assessed at pre-test to describe the sample. Specifically, participants will be asked to note when they were last physically active, how many times they have stopped being active, and what were the reasons for stopping activity.
2. Meaning Salience. Meaning salience is a primary outcome for Aim 2. The Meaning Awareness Scale (MAS) is a 6-item measure that assesses meaning salience.⁶³ Participants rate the extent to which they were aware of meaning over the past day (e.g., “I was aware of the meaning in my life” on a 7-point Likert type scale ranging from 1 (*rarely*) to 7 (*very often*)). Items are summed for a total score. Participants will complete the MAS on three random days during each of the four assessment periods and total scores will be averaged across those three days.
3. Basic Psychological Needs Satisfaction. Basic needs satisfaction is a primary outcome for Aim 2. The Psychological Needs Satisfaction in Exercise Scale (PNSE)⁶⁴ will be used to measure satisfaction of needs of autonomy (e.g., “I feel free to exercise in my own way”), competence (e.g., “I feel confident in my ability to perform exercises that personally challenge me”), and relatedness (e.g., “I feel attached to my exercise companions because they accept me for who I am”) in exercise contexts. The PNSE has 18-items that participants rate on a 6-point Likert-type scale ranging from 1 (false) to 6 (true). Items are averaged within and across the subscales for total scores. Previous research has demonstrated that the PNES has strong internal consistency reliability ($\alpha \geq .90$), construct validity, and convergent validity.⁶⁴
4. Internal Motivation. Internal motivation is a primary outcome for Aim 2. Motivation internalization will be measured using the Behavioral Regulations in Exercise Questionnaire, version 4 (BREQ-4).⁶⁵⁻⁶⁷ The 28-item BREQ-4 assesses motivations for exercise on the SDT continuum. There are 7 subscales with 4 items each: amotivation (e.g., “I don’t see why I should have to exercise.”); external regulation (e.g., “I exercise because other people say I should.”); introjected regulation-avoidance (e.g., “I feel guilty when I don’t exercise.”); introjected regulation – approach (e.g., “I

feel proud of myself when I persist.”); identified regulation (e.g., “It’s important to me to exercise regularly.”); integrated regulation (e.g., “I exercise because I value the benefits it gives me.”); and intrinsic motivation (e.g., “I exercise because it’s fun.”). The subscales will be combined using a bifurcation approach⁶⁸ and scored into two subscales: autonomous and controlled motivation. Autonomous regulation will be the average of the intrinsic, integrated, and identified scales whereas controlled regulation will be the average of the external and introjected scales. The BREQ-2 has been shown to have good psychometric properties, including good internal consistency (as range from .78 - .93).^{65,67}

5. **Mood.** Positive and negative mood will be measured using a positive and negative affect scale previously used in a study of daily meaning and daily mood.²⁷ Eight items will measure positive affect (relaxed, proud, excited, appreciative, enthusiastic, happy, satisfied, and curious) and five items will measure negative affect (sluggish, afraid, sad, anxious, and angry). Participants will rate their mood using a 5-point Likert-type scale ranging from 1 (*very slightly or not at all*) to 5 (*extremely*). Sums of the positive and negative affect scales have been shown to be positively correlated with their respective scales on the Positive and Negative Affect Schedule (PANAS)⁶⁹ ($r = .55 - .57$) and to have very high internal consistency ($\alpha = .97 - .98$). Participants will complete the mood scale on three random days during each of the four assessment periods and total scores will be averaged across those three days. Mood will be a covariate for Aim 2.
6. **Psychological Well-Being.** Psychological well-being will be assessed as an exploratory outcome. Well-being will be measured using two scales: The Subjective Vitality Scale (SVS)⁷⁰ and The Satisfaction with Life Scale (SWLS).⁷¹ The 6-item SVS measures feeling active, alive, enthusiastic, and energetic (e.g., “*I feel alive and vital*”). Participants will rate the extent they generally feel this way on a 7-point Likert-type scale ranging from 1 (*not at all true*) to 7 (*very true*). Items will be summed for a total SVS score. Previous psychometric studies have demonstrated that the SVS correlates positively with other positive measures of well-being (e.g., self-esteem, self-actualization, satisfaction with life) and negatively with poor psychological well-being (e.g., depression, anxiety, psychopathology), and was internally consistent ($\alpha = .84 - .86$).⁷⁰ On the SWLS, participants will rate their agreement with five statements on a 7-point Likert scale ranging from 1 (*strongly disagree*) to 7 (*strongly agree*). Responses will be summed so that higher scores correspond with greater satisfaction with life. Diener and colleagues⁷¹ conducted a thorough assessment of the SWLS’s reliability and validity. Previous assessments of reliability indicated that this measure is internally consistent ($\alpha = .87$) and had good two-month temporal stability ($r = .82$). Evidence for construct validity indicates that the SWLS correlated positively with other measures of subjective well-being and negatively correlated with measures of personality psychopathology. Evidence for criterion validity indicates that the measure correlated highly with interviewer’s rating of the individual’s satisfaction with life.⁷¹
7. **Text Message Acceptability.** Participants will rate the extent to which the text messages reflected what they found meaningful to them and their plans for physical activity. They will also report on the acceptability of the timing and frequency of the text messages at the end of the study. Participants will rate the extent to which they agree with each statement on a scale from 1 (strongly disagree) to 5 (strongly agree). Item responses will be analyzed separately.

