In Phase 1, we will develop the MAP to Health online web-based interview that will be used to explore what is particularly meaningful to participants, how PA is consistent with those goals, and what activities patients plan to engage in. Participants (N=12) will complete the interview and rate the ease of use, usefulness, intention to use, and theoretical fidelity of the intervention.

In Phase 2, we will conduct a proof-of-concept pilot trial using a double-pretest single group design. Participants (N=35) will complete a 4-week pretest monitoring period and an 8-week pilot trial of the intervention, with assessments of SDT mechanisms and meaning salience at pretest (-4 weeks), baseline (0 weeks), midpoint (4 weeks) and posttest (8 weeks). In addition, participants will wear accelerometers to assess PA during the 12 weeks.

2. Study Aims

Aim 1 (Development): To assess the acceptability of underlying theoretical and technological frameworks of the web-based MAP to Health interview.

H1a: Participants will rate the web-based interview as easy to use and useful and will report intentions to use the intervention.

H1b: The web-based interview will solicit data necessary to program theory-based, personalized text messages for participants.

Aim 2 (Proof-of-concept testing): To determine whether MAP to Health is related to changes in theoretically identified behavior change mechanisms.

H2: Participants will experience increases in the theoretically identified mechanisms of behavior change (i.e., meaning salience, internal motivation, and basic needs satisfaction) after receiving the MAP to Health intervention compared to a pre-test no intervention period.

Exploratory Aim: To assess whether the intervention and increases in the hypothesized behavior change mechanisms (meaning salience, internal motivation, and basic needs satisfaction) are associated with increases in PA compared to the pretest no intervention period.

3. Background, Rationale, Significance

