Potential participants will be identified through HP EHR by a Research Informatics Programmer Analyst. The Programmer Analyst will use the inclusion/exclusion list to determine potentially eligible participants. The Programmer Analyst will exclude participants who have opted out of research as well as anyone who was involved in Phase 1. Additional recruitment may be conducted in collaboration with the HP Communications team through social media posts or press releases.

2. Recruitment & Screening:

Potential participants identified through the EHR will be mailed a letter that describes the study and invites them to participate. Interested individuals will have the option to complete an online screener to determine if they are eligible or call the study team if they are interested, or they can wait for a phone call from CESR staff. A CESR survey specialist will talk with potentially eligible participants via phone to screen for additional eligibility requirements. Specifically, they will ask questions about recent physical activity, interest in increasing activity, readiness for physical activity (Physical Activity Readiness Questionnaire), alcohol use (AUDIT-C), consistent access to a smartphone with text-messaging capability, and access to internet (through phone or computer). If individuals are eligible, CESR staff will schedule participants for a study orientation visit with the Project Manager and send them a study confirmation email with a link to the web-based platform, which will contain an e-consent form, and a detailed list of study activities. **See Appendix D for Phase 2 recruitment materials.**

3. Outcome Assessments:

Participants will complete survey measures at 4 time points: pre-test (-4 weeks), baseline (0 weeks), midpoint (4 weeks), and posttest (8 weeks). To improve retention, we will send regular text and email reminders to complete study activities (up to 3 per assessment). If participants have not completed surveys after email and text prompts, the Project Manager may make one follow-up phone call to encourage completion.

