- a. Pretest (-4 weeks): After reviewing the e-consent form, participants will complete the Pretest survey measures in REDCap through the MAP to Health web-based platform. Participants will complete measures of the hypothesized intervention mechanisms (basic psychological needs satisfaction and internal motivation) as well as demographic and physical activity history measures that will be used to describe the sample. During the study orientation visit, the Project Manager will confirm that participants have completed the Pretest survey and will mail participants the accelerometer. During the orientation visit, the Project Manager will review instructions for the accelerometer, including instructions on how to wear it, charge it, and ensure that the data are synced to the cloud-based data management software (CentrePoint). The Project Manager will follow-up with the participants within 2-3 business days by phone to ensure the participants received the accelerometer and understand how to use it. The Project Manager will monitor ActiGraph data collection and will contact participants if data have not been uploaded for more than 2 consecutive days to encourage charging and/or wear. The Project Manager will schedule the remaining assessment surveys in REDCap for the participants. In the week following the Pretest surveys, participants will complete measures of meaning salience and mood on three random days (2 weekdays and 1 weekend day).
- b. Baseline (0 weeks): In the week leading up to baseline, participants will be sent the measures of meaning salience and mood on three random days (2 weekdays and 1 weekend day). They will be prompted to complete the baseline surveys that assess hypothesized mechanisms (basic needs satisfaction and internal motivation). Once the baseline survey measures are complete, the web-based platform will prompt participants to complete the MAP to Health web-based interview and start the intervention.
- c. Midpoint (4 weeks): In the week leading up to the midpoint assessment, participants will be prompted to complete the measures of meaning salience and mood on three random days (2 weekdays and 1 weekend day). They will be prompted to complete the midpoint surveys that assess hypothesized mechanisms (basic needs satisfaction and internal motivation).

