d. **Posttest (8 weeks):** In the week leading up to the posttest assessment, participants will be prompted to complete the measures of meaning salience and mood on three random days (2 weekdays and 1 weekend day). They will be prompted to complete the posttest surveys that assess hypothesized mechanisms (basic needs satisfaction and internal motivation). Participants will provide feedback on intervention and study procedures using the measures from Phase 1 (usability and intervention fidelity).

4. Exit Interview

After Week 12, the Project Manager will call each participant to conduct an exit interview over the phone. The interview will consist of open-ended questions about the participant's experience with the study. After the interview, the Project Manager will confirm that the participant has returned the accelerometer to the study or provide instruction on how to complete the return.

5. Incentives

Participants can receive up to \$250 for their participation. Incentives will be paid out based on the activity schedule (**see Appendix D: Phase 2 Activities and Incentives Schedule**). Incentives will be distributed every 4 weeks. The Project Manager will upload the final incentive disbursement at the end of the study, prorated based on the return of the accelerometer.

[figure not shown]
d. MAP to Health Intervention

i. Intervention Overview

The Meaningful Activity Program (MAP to Health) intervention is a theory-driven mobile health (mHealth) intervention that has the goal of helping adults in midlife increase physical activity. Specifically, MAP to Health uses theory (see Figure 3) and mHealth technology to increase **meaning salience** and support **basic psychological needs** (support autonomy in PA activities, encourage setting small goals to increase competence, and encouraging relatedness through promoting PA activities with important others), which will, in turn, enhance **internal motivation** to engage in PA. By explicitly addressing meaning, the intervention will overtly integrate PA with key life values, and therefore increase the likelihood that PA will become internally motivated and maintained. The intervention will be

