Aim 2 Analysis. The goal of Aim 2 is to determine whether the intervention satisfactorily impacts the hypothesized theoretical mechanisms. As an exploratory outcome, we will also assess PA. Participant ratings of meaning salience (average of 3 measures across the week), basic psychological needs satisfaction, and internal motivation will each be compared across four time points (weeks -4, 0, 4, 8) using multilevel linear modeling with time points nested within participants to control for repeated measures variance. A fixed time effect will estimate participant ratings at each time point relative to baseline, and a series of linear contrasts will test our hypotheses about the pattern of change in ratings over time. Without intervention, we do not expect to see change in hypothesized mechanisms so that a week -4 vs. week 0 contrast will be close to zero. Following intervention implementation, however, we expect participants to report increases in the theoretical mechanisms so that contrasts comparing weeks 4 and 8 to baseline will each be positive. Furthermore, we expect to see the greatest change in the first 4 weeks post-intervention so that a week 8 vs. week 4 contrast will be close to zero.

Exploratory Aim Analysis. In exploratory analyses, we will use this same approach as Aim 2 to examine changes in PA and whether the hypothesized mechanisms are related to PA over time (i.e., pre-intervention, early intervention, and late intervention stages). First, we will examine whether the difference in PA slope during the active intervention phase (week 0 to week 8) is significantly greater than the change observed during the pre-intervention phase. Additionally, we will examine whether changes in hypothesized mechanisms (meaning salience, needs satisfaction, and internal motivation) from week 0 to week 4 are associated with changes in PA from week 0 to week 8 using growth curve modeling. Although this pilot study will not be powered to determine statistical significance, the effect sizes will be calculated to assess the extent to which the intervention is impacting the hypothesized mechanisms.

g. Power analysis

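### Meaning salience is sampled after the pretest survey but before every later one, so its no-intervention interval is about 20 days against 28 days after baseline

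*Combined protocol and SAP*

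**What the plan says.** The Summary (Section 1) describes a double-pretest design in which participants "will complete a 4-week pretest monitoring period and an 8-week pilot trial of the intervention". H2 (Section 2) expects the mechanisms to rise "after receiving the MAP to Health intervention compared to a pre-test no intervention period". There is no control group.

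The sampling days for meaning salience and mood are set out in Section 4.c.v, Phase 2, Outcome Assessments:

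- Pretest: "In the week following the Pretest surveys, participants will complete measures of meaning salience and mood on three random days".
- Baseline: "In the week leading up to baseline, participants will be sent the measures of meaning salience and mood on three random days".
- Midpoint: "In the week leading up to the midpoint assessment, participants will be prompted to complete the measures of meaning salience and mood".
- Posttest: "In the week leading up to the posttest assessment, participants will be prompted to complete the measures of meaning salience and mood".

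Section 4.a.ii says only that the three days lie in the same weeks as the main assessments, and Section 4.e.iv only that they lie in each assessment period. Neither says before or after. Section 4.e.iv makes meaning salience a primary Aim 2 outcome, scored as the mean of three daily totals, and makes mood an Aim 2 covariate.

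The Aim 2 analysis (Section 4.f) labels all three mechanisms weeks -4, 0, 4 and 8, and expects that "a week -4 vs. week 0 contrast will be close to zero".

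**The concern.** The pretest period is the only control in this trial. It serves best when it is as long as the periods it is compared with, because any natural change then has equal time to appear in each. Needs satisfaction and internal motivation are taken from the surveys and keep the nominal spacing. Salience does not: its pretest days move forward into the control period, while its baseline days stay ahead of the week 0 survey. Both shifts shorten the control interval, yet the analysis labels make it look like four weeks.

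At stake is the size comparison behind H2. Section 4.g says the aim is to judge how large the changes are rather than to establish statistical significance. A pretest change measured over a shorter time, read beside a 28-day change after baseline, makes salience look more stable without intervention than it may be.

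**Working it through.** **The plan's own figure.** Section 4.g gives d ≥ 0.49 as detectable with N = 35, power 0.80 and alpha 0.05 in a paired t-test. With a two-sided test, power at d = 0.49 is 0.804 and the smallest detectable d is 0.487, so the figure reproduces. It does not depend on the sampling windows. It is relevant here only because Section 4.g ties it to a week -4 vs week 0 difference of about zero.

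**Inputs.** Survey days are -28, 0, 28 and 56 (Section 4.c.v, weeks -4, 0, 4 and 8). This assumes that the baseline survey falls exactly 28 days after the pretest survey. Each sampling window is 7 days.

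**Window centres and gaps.**

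| Assessment | Window, survey day excluded | Centre | Window, survey day included | Centre |
|---|---|---|---|---|
| Pretest | -27 to -21 | -24 | -28 to -22 | -25 |
| Baseline | -7 to -1 | -4 | -6 to 0 | -3 |
| Midpoint | 21 to 27 | 24 | 22 to 28 | 25 |
| Posttest | 49 to 55 | 52 | 50 to 56 | 53 |

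- Survey day excluded: -4 - (-24) = 20 days; 24 - (-4) = 28 days; 52 - 24 = 28 days.
- Survey day included: -3 - (-25) = 22 days; then 28 and 28 days.
- Survey day counted on one side only: 21 days for the first gap.

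The value labelled week -4 therefore sits near week -24/7 = -3.4. The three later values are each shifted by the same 4 days, which is why their spacing stays at 28.

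**Random days.** Enumerating every draw of two weekdays and one weekend day, for each starting weekday, gives a mean control interval of 19.8 to 20.1 days. Individual three-day means lie 16.7 to 24.0 days apart before baseline, and 24.0 to 32.0 days apart from baseline to midpoint.

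**Share of drift captured.** Under steady linear drift with no intervention effect, the share is the interval divided by 28: 20/28 = 0.71 and 22/28 = 0.79.

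**Sensitivity to the anchor.** If baseline were timed from a point k days after the pretest survey while salience sampling stayed tied to that survey, the interval would be 20 + k: 23 days for k = 3 and 27 days for k = 7. The survey measures would then have 28 + k days.

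**Rescaling.** Pretest change per 28 days is the observed change times 28/20 = 1.4 (28/22 = 1.27 on the longer count). Its standard error scales by the same factor, so the ratio of estimate to standard error is unchanged.

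**The case against.** The strongest reply is that the Aim 2 model is not harmed. Section 4.f estimates each time point relative to baseline and then forms contrasts. That coding assumes nothing about spacing. A reader might infer that the model wrongly treats the points as equally spaced, or that the week 4 and week 8 effects are biased; the documents support neither. The pre- against post-intervention slope comparison in Section 4.f is written for physical activity, and for the mechanisms the plan lists no subtraction of pretest change from week 0 to 4 change. This stands. What remains is that H2 still calls for that comparison.

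The ordering is also largely forced. E-consent must precede study activities (Section 4.c.iii), so pretest days cannot come earlier. Completing the baseline survey leads straight into the intervention, so baseline days cannot come later. This explains the mismatch but does not remove it.

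The exact interval is not certain. The plan does not say from which event the four weeks are counted, and the study-design figure and activities schedule are not visible in the text available. This also stands, and is a further reason to work from actual dates.

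Finally, salience is described as a state that varies within a day, and nothing in the documents shows that it drifts. A reader might infer that a definite number of scale points would be credited to the intervention. That would need an assumed drift as well as a subtraction the plan does not list.

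**Conclusion.** The point holds in limited form. For meaning salience and mood, the pretest contrast spans about 20 days (21 to 22 if survey days count) and not the stated four weeks, provided the pretest and baseline surveys are 28 days apart. Nothing in the visible text acknowledges this. If drift were steady, the contrast would show about 71% to 79% of what a 28-day interval shows. The contrasts of weeks 4 and 8 with baseline are unaffected, and needs satisfaction and internal motivation keep their 28-day spacing under the same assumption. The size of any bias in the H2 comparison is unknown, because the documents give neither a drift nor an SD for salience. It is worth correcting because this is the only control interval for a primary outcome, in a pilot that will be read on the size of change.

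**What to change.** For meaning salience and mood, the SAP should:

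- use the actual sampling dates and report the true pretest-to-baseline interval;
- wherever pretest change is compared with week 0 to 4 change, make the comparison per equal time. Either fit pre- and post-baseline slopes on actual dates, or give pretest change per 28 days with its standard error scaled likewise. State the linearity assumption in either case;
- reconcile the time labels in Sections 4.a.ii, 4.c.v, 4.e.iv and 4.f, so that the first salience value is not presented as week -4 without comment.

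This changes analysis wording only. The cost is precision: at 20 days the confidence interval on the per-28-day pretest change is 1.4 times as wide. The scaling does not change the test against zero and should not be presented as making that check stricter.

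Moving the baseline survey so that the two salience weeks are 28 days apart is not recommended. It would add 6 to 8 days (28 - 22 to 28 - 20), giving needs satisfaction and internal motivation a pretest interval of about 35 days against 28 afterwards. That would pass the mismatch from one primary outcome to two.
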